**The following Amendment(s) and Administrative Changes have been made to this protocol since the date of preparation:**

Amendment No.	Date of Amendment	Local Amendment No:	Date of Local Amendment
_____	_____	_____	_____
_____	_____	_____	_____

Administrative Change No.	Date of Administrative Change	Local Administrative Change No.	Date of Local Administrative Change
_____	_____	_____	_____
_____	_____	_____	_____
_____	_____	_____	_____

## PROTOCOL SYNOPSIS

---

### **Antiplatelet therapy effect on platelet extracellular vesicles in acute myocardial infarction (AFFECT EV)**

---

#### **Principal Investigator**

**[name]**

#### **Study site(s) and number of subjects planned**

1st Chair and Department of Cardiology, Medical University of Warsaw, 60 subjects

---

Study period		Phase of development
Estimated date of first subject enrolled	28.12.2016	4
Estimated date of last subject completed	28.12.2017	4

---

#### **Study design**

This is a prospective, single-centre, randomised, open-label, parallel group design, phase 4, proof-of-concept study conducted at the 1st Chair and Department of Cardiology, Medical University of Warsaw, Poland. The analytical part will be conducted in the Vesicle Observation Centre, Academic Medical Centre, University of Amsterdam, The Netherlands. The duration of this study is expected to be 12 months.

#### **Objectives**

Primary Objective:	Outcome Measure:
---------------------------	-------------------------

To compare the effects of ticagrelor and clopidogrel on the concentration of PEVs in patients with acute myocardial infarction.
	
Concentration of PEV exposing P-selectin and PS (flow cytometry).

--	--

Secondary Objective:	Outcome Measure :

To compare the effects of ticagrelor and clopidogrel on the concentration of EVs exposing fibrinogen, exposing phosphatidylserine, EVs from endothelial cells, EVs from leukocytes.
	
Concentration of EV exposing fibrinogen, exposing phosphatidylserine, EVs from endothelial cells, EVs from leukocytes.

Safety Objective:	Outcome Measure :

To evaluate the safety and tolerability of ticagrelor in relation to clopidogrel. To be reported descriptively.
	
 
- Vital signs
 
- Abnormal blood tests values (haematology and clinical chemistry)
 
- Abnormal values in urinalysis
 
- Abnormalities in 12-lead ECG
 
- AEs/ SAEs
 

### **Target subject population**

Subjects with the first ST-elevation acute myocardial infarction (STEMI) or non-STEMI (NSTEMI) who underwent percutaneous coronary intervention (PCI) with stent implantation and received a loading dose of clopidogrel (600 mg) prior to PCI.

### **Duration of treatment**

6 months

### **Investigational product, dosage and mode of administration**

All drugs, including the investigational product ticagrelor, will be administered orally. All subjects will be administered a loading dose of clopidogrel (600 mg) prior to PCI. Subjects randomised to ticagrelor will receive a loading dose of ticagrelor (180 mg), followed by a maintenance dose (90 mg twice daily). Subjects randomised to clopidogrel will continue the treatment with a maintenance dose of clopidogrel (75 mg once daily). According to the guidelines of European Society of Cardiology, double antiplatelet therapy with acetylsalicylic acid (ASA) and a P2Y12 receptor antagonist will be continued for 12 months. The study treatment will last for 6 months until the last visit at the end of the treatment (LSLV). After termination of the study patients will be prescribed double antiplatelet therapy for the remaining 6 months. Ticagrelor will be recommended over clopidogrel. Subjects who choose to switch to clopidogrel due to financial constraints will be prescribed clopidogrel.

### **Statistical methods**

Categorical variables will be presented as number (%); continuous variables will be presented as mean and standard deviation (SD) or median with inter-quartile range. Shapiro–Wilk test will be used to test for non-Gaussian distribution of continuous variables. Student's two-sided t-test or ANOVA-repeated measures will be used for normally distributed values. Mann–Whitney U test or Friedman test will be used for variables without normal distribution. A p-value below 0.05 will be considered significant.

## LIST OF APPENDICES

Appendix A Signatures

Appendix B Bioethical Committee Approval and Amendment (in Polish)

Appendix C Patient Information Sheet and Consent Form (in Polish)

Appendix D Protocol for blood collection and handling

Appendix E Conference abstract and sample size calculation

## LIST OF ABBREVIATIONS AND DEFINITION OF TERMS

The following abbreviations and special terms are used in this study Clinical Study Protocol.

Abbreviation or special term	Explanation
AE	Adverse event
CRF	Case Report Form (electronic/paper)
CSA	Clinical Study Agreement
CSR	Clinical Study Report
CTCAE	Common Terminology Criteria for Adverse Event
DAE	Discontinuation of Investigational Product due to Adverse Event
DNA	Deoxyribonucleic acid
EC	Ethics Committee, synonymous to Institutional Review Board (IRB) and Independent Ethics Committee (IEC)
GCP	Good Clinical Practice
ICH	International Conference on Harmonisation
IP	Investigational Product
IVRS	Interactive Voice Response System
IWRS	Interactive Web Response System
LSLV	Last Subject Last Visit
OAE	Other Significant Adverse Event
PGx	Pharmacogenetic research
PI	Principal Investigator
SAE	Serious adverse event
WBDC	Web Based Data Capture

## **1. INTRODUCTION**

### **1.1 Background and rationale for conducting this study**

Platelet activation and aggregation in response to atherosclerotic plaque rupture is a key event in the pathogenesis of acute myocardial infarction (AMI) [1]. Platelet P2Y12 receptors for adenosine diphosphate are essential for platelet activation [2], and from this reason antagonists against the P2Y12 receptor are established in secondary prevention of cardiovascular events [3]. Beyond blocking platelet activation, antagonists of the P2Y12 receptor have hitherto unexplained anti-inflammatory effects [4,5]. Findings from the PLATelet inhibition and patient Outcomes (PLATO) study demonstrated that platelet inhibition with a novel and potent P2Y12 receptor antagonist ticagrelor reduced mortality following pulmonary infections and sepsis compared to clopidogrel, previous standard treatment for patients with AMI [5].

Activated platelets release platelet extracellular vesicles (PEV) [6]. PEV differ from other biomarkers of inflammation and platelet activation, because (i) PEV are released from activated platelets at the early stage of developing arterial thrombosis [7], (ii) PEV expose specific platelet antigens and thus can be identified as being platelet-specific [8], (iii) PEV participate both in inflammation and in coagulation due to exposure of P-selectin and phosphatidylserine (PS) [9,10]. P-selectin initiates binding of platelets and/ or PEV to leukocytes which leads to leukocyte activation and secretion of cytokines [9], and (ii) PS and other negatively charged phospholipids bind positively charged clotting factors thereby propagating thrombin generation [10]. Additionally, PEV serve as pro-inflammatory stimuli in acute lung injury [11], which is one of the leading causes of death in sepsis [12]. Because identification and characterization of PEV directly in human plasma has recently become feasible [13], and because PEV can be measured in biorepositories thereby facilitating validation in multicentre clinical trials [14], it is likely that the requirements for PEV to become a reliable biomarker can now be fulfilled.

## 1.2 Rationale for study design, doses and control groups

### *Rationale for study design*

Clinical studies suggest that platelet P2Y12 receptor antagonists exert anti-inflammatory effects [4,5], but the underlying mechanisms have not been clearly defined *in vivo*. This study is expected to identify an additional mechanism of action of the P2Y12 antagonist ticagrelor (inhibition of PEV release), which might partly explain the lower rate of infection-related mortality in patients treated with ticagrelor, compared to clopidogrel [5]. Regarding the exponentially growing interest in the field of EV in the last decade [6,13,14], as well as the crucial role of PEV in inflammation and thrombosis [9,10], determining the effect of ticagrelor on PEV release is an important step in cardiovascular pharmacology research. Although the study is preliminary in the design and not powered for mortality, the results are expected to pave the road for further studies designed to investigate the association between concentrations of PEV and infection-related mortality in patients treated with ticagrelor, and facilitate the development of PEV-based pharmaceuticals with applications in atherosclerosis-related cardiovascular diseases.

The randomised and investigator-blinded allocation to the study groups along with state-of-the art methods of PEV analysis will account for the reliability of results. The study will be conducted in the 1st Chair and Department of Cardiology, Medical University of Warsaw, Poland. The analytical part will be conducted in the Vesicle Observation Centre, Academic Medical Centre, University of Amsterdam, The Netherlands. The involvement of experts with a track record on extracellular vesicles from the Netherlands ([name], [name]) will ensure a scientifically sound project and optimize dissemination of results.

### *Doses*

All drugs will be administered orally, in doses recommended by European Society of Cardiology in the Guidelines on Myocardial Revascularization [3]. If not already administered prior to hospital admission, patients will receive a loading dose of clopidogrel (600 mg) prior to percutaneous coronary intervention (PCI). Patients randomised to ticagrelor will receive a loading dose of ticagrelor (180 mg), followed by a maintenance dose (90 mg twice daily).

Patients randomised to clopidogrel will continue the treatment with a maintenance dose of clopidogrel (75 mg once daily).

### *Control group*

[figure not shown]
- Patients randomised to clopidogrel.

### *Benefit/risk and ethical assessment*

All study drugs are administered on-label. According to the Guidelines on Myocardial Revascularization, both in subjects with STEMI and NSTEMI ticagrelor is recommended over clopidogrel, and clopidogrel is recommended when ticagrelor is not available or is contraindicated [3]. Because ticagrelor is not reimbursed in Poland, it is not available for the majority of Polish patients due to financial constraints. Participation in the study ensures the free access to ticagrelor for patients randomized to the study group during the first 6 months after AMI, which is the period of the highest risk of recurrent major adverse cardiovascular events (MACE) [15,16]. Participation in the study ensures also the free access to clopidogrel for patients randomized to the control group during the first 6 months after AMI. All patients will undergo an additional cardiovascular investigation at the last visit at 6 months.

## 1.3 Study Design

Figure 1. Study flow chart.

Blood: Platelet extracellular vesicles, aggregometry

Abbreviations: AMI – acute myocardial infarction; PCI – percutaneous coronary intervention;

ASA – acetylsalicylic acid; R – randomization, QD – once daily; BID – twice daily

## 2. STUDY OBJECTIVES

### 2.1 Primary objective

Primary Objective:	Outcome Measure:
To compare the effects of ticagrelor and clopidogrel on the concentration of PEVs in patients with acute myocardial infarction.	Concentration of PEV exposing P-selectin and PS (flow cytometry).

### 2.2 Secondary objectives

Secondary Objective:	Outcome Measure :
To compare the effects of ticagrelor and clopidogrel on the concentration of EVs exposing fibrinogen, exposing phosphatidylserine, EVs from endothelial cells, EVs from leukocytes.	Concentration of EV exposing fibrinogen, exposing phosphatidylserine, EVs from endothelial cells, EVs from leukocytes.

### 2.3 Safety objectives

Safety Objective:	Outcome Measure :
To evaluate the safety and tolerability of ticagrelor in relation to clopidogrel. To be reported descriptively.	

- Vital signs

- Abnormal values in blood tests ( haematology and clinical chemistry)

- Abnormal values or in urinalysis

- Abnormalities in 12-lead ECG

- AEs/ SAEs

## 2.4 Exploratory objectives

Exploratory Objective:	Outcome Measure :
To identify an additional mechanism of action of ticagrelor, which may at least in part explain the lower rate of infection-related mortality in patients treated with ticagrelor, compared to clopidogrel.	Concentration of PEV exposing P-selectin and phosphatidylserine (PS).

## 3. SUBJECT SELECTION, ENROLMENT, RANDOMISATION, RESTRICTIONS, DISCONTINUATION AND WITHDRAWAL

### 3.1 Inclusion criteria

- Age > 18 years
- Informed consent to participate in the study
- PCI due to first ST-elevation myocardial infarction (STEMI) or non-STEMI (NSTEMI)
- Administration of the loading dose of clopidogrel (600 mg) prior to PCI

### 3.2 Exclusion criteria

- Known coagulopathy
- Active pathological bleeding
- Known history of bleeding disorder
- Suspicion of intracranial haemorrhage
- Need for oral anticoagulation therapy
- Administration of GPIIb-IIIa antagonists
- Cardiogenic shock
- Severe chronic renal failure (eGFR < 30 mL/min)
- Severe liver insufficiency
- Infectious disease
- Autoimmune disease

- Neoplasm
- Chronic dyspnea
- Increased risk of bradycardia
- Known pregnancy, breast-feeding, or intention to become pregnant during the study period
- Study drug intolerance
- Co-administration of ticagrelor or clopidogrel with strong CYP3A4 inhibitors
- Participation in any previous study with ticagrelor or clopidogrel

### **3.3 Subject enrolment and randomization**

Subjects will be enrolled by the PI at the 1st Chair and Department of Cardiology, Medical University of Warsaw. Subjects will be randomized by an independent operator at 1st Department of Cardiology, Medical University of Warsaw. Randomisation will be carried out in 1:1 ratio using block randomization via the mobile application “Randomizer for Clinical Trial” (Medsharing, France).

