## **8.2 Sample size**

Because there is no sufficient data to assess the impact of ticagrelor on the concentrations of PEV in patients with AMI, the SD and mean difference between the groups was estimated based on the preliminary experiments, which we conducted in during preparation for this study. The required sample size was calculated by a two-sided t-test at a significance level of 0.05 with the following assumptions: (i) SD in each group  $\pm 1$ , (ii) mean difference between the groups = 1, (iii) nominal test power = 0.9. Based on this sample size estimation, it is calculated that a total of 60 patients will be enrolled in the trial. The conference abstract [15], as well as the explanation on how the sample size has been calculated are included in Appendix E.

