### **8.3.5 Analysis of the primary variable(s)**

Primary variable is the concentration of PEV exposing P-selectin and PS. Student's two-sided t-test or Mann–Whitney U test will be used to compare the concentrations between the two treatment arms. ANOVA-repeated measures or Friedman test will be used to compare the concentrations between the three blood samplings for PEV analysis within each group. A p-value below 0.05 will be considered significant.

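### Infarct type (STEMI or NSTEMI) is known at entry but is named in neither the randomisation nor the between-arm test; prespecifying adjustment for it is a cheap, optional gain in precision and interpretability

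*Combined protocol and SAP*

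**What the plan says.** Section 3.1 admits patients with either type of infarct: "PCI due to first ST-elevation myocardial infarction (STEMI) or non-STEMI (NSTEMI". It sets no quota and gives no expected share of either type.

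Section 3.3 describes allocation: "Randomisation will be carried out in 1:1 ratio using block randomization via the mobile application". It states no stratification factor and no block size. It does not rule stratification out; it is silent.

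For the primary variable, Section 8.3.5 says "Student's two-sided t-test or Mann–Whitney U test will be used to compare the concentrations between the two treatment arms", and Section 8.3.6 repeats this for the secondary variables. Neither section names a covariate. Sections 8.3.7 and 8.3.9 mark subgroup and sensitivity analyses as not applicable. Section 8.3 does list an analysis of baseline characteristics, so an imbalance could be seen there, but no planned analysis would respond to it.

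The schedule in Section 4 checks eligibility at Visits 1 and 2 and randomises at Visit 2. Because infarct type is part of an inclusion criterion, it is known for every subject when the arm is assigned.

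**The concern.** Blocks keep the arm totals equal. They do not keep the STEMI share equal across arms unless they are run within infarct type. With about 30 patients per arm, a visible difference in case mix can arise by chance.

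The primary marker is a product of platelet activation. Section 1.1 describes these vesicles as released early in developing arterial thrombosis, and Section 5.7 places two of the three samples soon after the event. It is therefore plausible, though not documented, that infarct type shifts the concentration. If it does, two things follow. The variance between types stays in the error term. And if the arms are visibly unequal in STEMI share, the plan has no prespecified answer, while an adjustment chosen after seeing the imbalance would be open to challenge.

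**Working it through.** **Inputs from the plan (Section 8.2).** The sample size was "calculated by a two-sided t-test at a significance level of 0.05", with "mean difference between the groups = 1", an SD of 1 per group and "nominal test power = 0.9". The stated result is that "a total of 60 patients will be enrolled in the trial". At 1:1 this is 30 per arm, which is inferred rather than stated.

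**The plan's own figure.** The normal formula is n per arm = 2(1.960 + 1.282)² × (1/1)² = 21.01, so 22 per arm or 44 in total. The exact t-test needs 23 per arm or 46 in total (power 91%). The stated 60 does not follow from the stated inputs; with 30 per arm the power is 97%. Appendix E, which explains the calculation, is not in the text available. This is a separate matter. Here it shows only that the planned comparison has power to spare at a difference of 1 SD.

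**Assumptions, none given in the documents.** STEMI share 50% (30% and 70% also tried); difference between types of 0, 0.3, 0.5 or 1.0 SD; blocks of 4 in the simulation; normally distributed data; complete data on 30 per arm.

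**Step 1: how often the arms are imbalanced.** A gap of 20 points is 6 of 30 patients.
- If the STEMI total varies by chance, P(|X₁ − X₂| ≥ 6) for two independent Binomial(30, 0.5) counts is 15.5%. At 30% or 70% STEMI it is 12.0%.
- If exactly 30 of the 60 have STEMI, the hypergeometric probability is 19.6%. If exactly 18 or 42 do, it is 15.8%. The figures differ partly because a fixed even total allows only even gaps.
- With 30 of 60 STEMI, the SD of the gap is 13 points and a gap of 30 points or more has probability 1.9%.

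**Step 2: what such a gap does to the estimate.** Shift = gap × difference between types = 0.20 × 0.3, 0.5 or 1.0 = 0.06, 0.10 or 0.20 SD. The standard error of the unadjusted difference is √(2/30) = 0.258 SD. On the plan's SD scale the shift is therefore 0.23, 0.39 or 0.77 standard errors.

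**Step 3: variance removed by adjustment.** With d the difference in within-type SDs and p = 0.5, the share is p(1 − p)d² / (1 + p(1 − p)d²):
- d = 0.3: 0.0225/1.0225 = 2.2%
- d = 0.5: 0.0625/1.0625 = 5.9%
- d = 1.0: 0.25/1.25 = 20%

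If the difference is instead expressed in the plan's per-group SD, which includes the variation between types, the share is p(1 − p)d² = 2.3%, 6.3% or 25%. The simulation below uses that scale.

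**Step 4: error rates and power at 30 per arm** (simulation, 40,000 trials under the null and 20,000 for power; t-test against a linear model with arm and infarct type).

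| Difference between types (SD) | Type I error, all trials: unadjusted / adjusted | Type I error, gap ≥ 20 points: unadjusted / adjusted | Power at 0.7 SD: unadjusted / adjusted | Power at 1 SD: unadjusted / adjusted |
|---|---|---|---|---|
| 0 | 5.0% / 5.0% | 5.2% / 5.2% | 76% / 75% | 97% / 96% |
| 0.3 | 4.8% / 4.8% | 5.5% / 4.8% | 76% / 76% | 97% / 97% |
| 0.5 | 4.9% / 5.0% | 6.5% / 5.1% | 76% / 78% | 97% / 97% |
| 1.0 | 5.0% / 5.1% | 12.7% / 5.3% | 76% / 86% | 97% / 99% |

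**The case against.** A reader might infer that the unadjusted comparison is biased, or that it confounds infarct type with drug. The documents do not support that. Allocation is random, the standard error already allows for chance imbalance, and type I error is about 5% over all randomisations. The rate rises clearly (to 12.7%) only when a gap of 20 points or more coincides with a difference of 1 SD between types.

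A reader might also infer that infarct type is an established predictor of the marker. No section says so. Section 1.1 treats acute infarction as one entity, and nothing in the plan ranks infarct type above other baseline factors. At 0.3 SD the gain is negligible, and at the planned difference of 1 SD power is already 97%. These points stand, and they limit the finding to an optional improvement.

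It can further be said that the first vesicle sample, taken 24 hours after the clopidogrel loading dose (Section 5.7), would be a more direct covariate. If it is drawn before study drug, it would carry much of any infarct-type effect already present, and infarct type might then add little. That is fair, but Section 8.3.5 does not use the first sample as a covariate either, and Section 5.7 does not place it relative to randomisation. The within-arm comparisons over time are unaffected by stable differences between patients, but they do not compare the arms.

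What survives is the asymmetry. Adjustment costs about one point of power if infarct type is irrelevant and gains up to about ten if it matters, both at a true difference of 0.7 SD.

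**Conclusion.** The plan enrols two infarct types, names no stratification factor and compares the arms without regard to type. The planned test is valid, so this is a matter of precision and of interpretation under visible imbalance. Under an assumed 50% STEMI share, an imbalance of 20 points or more has a probability of about 15% to 20%, and the shift it causes is below one standard error across the range considered. How much is gained depends on the difference between the types, which the documents do not give: nothing at zero, little at 0.3 to 0.5 SD, and a material amount near 1 SD. The point is an optional improvement, supported by its low cost rather than by any demonstrated fault.

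**What to change.** **Analysis.** In Sections 8.3.5 and 8.3.6, prespecify that the between-arm comparison accounts for infarct type as diagnosed at entry. Use a linear model with arm and infarct type, on the log scale if the data are skewed. Where the plan would use Mann–Whitney, use a rank test stratified by infarct type (van Elteren), so that the route for non-normal data is kept. Make the change before marker results are linked to arm, and name infarct type as a baseline item, since the schedule in Section 4 does not list it separately.

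**Randomisation.** Only if enrolment has not begun, also run separate 1:1 small-block lists for STEMI and NSTEMI in Section 3.3. If it has begun, leave allocation alone; the analysis change gives most of the benefit.

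**Cost.** The model uses one degree of freedom of 58. A log-scale model reports a ratio rather than a difference. Stratified lists need one extra field at randomisation, and arm totals may differ by up to half a block per stratum: up to 2 × 2 = 4 patients with blocks of 4, or 2 × 3 = 6 with blocks of 6.
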